The next phase of the study will occur primarily at home. During the 7 week run-in phase, participants will collect urine specimens and complete symptom questionnaires at 2 random intervals when prompted by the study co-ordinator. During week 8, there will be a study visit with the research staff. Participants will return samples collected at home along with an additional stool sample collected at week 8 which will be used for randomization to either continued double-blinding to biomarker detection or an open results arm. All participants will have a diet assessment in conjunction with the week 8 study visit. This will occur either in person or remotely by telephone or video link. During the last phase of the study (weeks 8-30), participants will be prompted to collect additional urine specimens and complete questionnaires at random intervals (~q 4 weeks). Participants in the open arm may also collect up to 4 additional stool samples during this time as well.

Participants in the open results arm will also be provided with home testing kits so that they may receive immediate qualitative (yes/no) feedback regarding the presence of biomarkers of gluten exposure in their stool and/or urine. Collection of urine samples will be initiated by the investigators. Collection and testing of stool samples will occur at times of the participants choosing. Participants may opt to test up to 4 stool samples, and will report test use date, results of the test, and reasons for use to the research team after each use. At the end of the 30 week study period, all participants will have a final study visit and an additional diet assessment by a Registered Dietitian. All participants will be unblinded to the results of biomarker testing after their samples have been processed. Blood will be collected and stored for testing of biomarkers of gluten-free diet adherence at the first study visit. If a participant agrees to blood sample collection at their third study visit, blood will also be collected at that time (weeks 0, and 30).

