##### Secondary outcomes:

- Difference in mean gluten exposure following randomization in blinded vs. open results groups. Mean gluten exposure is defined as the average per individual subject post-randomization concentration of gluten immunogenic peptides detected using the quantitative assay.
- Per individual change in frequency and quantity of gluten exposure pre- and post-randomization in blinded and open results groups.
- Symptom score (average for weeks 8 through 30 and at week 30) with blinded vs. open results of biomarker detection.

- Symptom score (average during run-in compared to week 30) with blinded vs. open results of biomarker detection.
- Change in celiac disease specific quality of life as measured by CDDUX between weeks 1 and 30 in blinded vs. open results groups.
- Change in health related quality of life between weeks 8 and 30 as measured by PedsQL core 4.0^37 in blinded vs. open results groups.
- Growth trajectory (weight, height and BMI) between weeks 8 and 30.
- Agreement between results of patient/parent performed qualitative testing and quantitative testing performed by research team
- Rate of school absences and missed extracurricular activities in blinded vs. open results group.

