During week 8, participants will bring samples collected at home and completed questionnaires to the second study visit along with an additional stool sample taken at the week 8 time point. At this time, there will be a blood draw and participants will be randomized to continue with double-blinded test results or an open results arm. Randomization will be stratified based upon the results of GIP testing in stool collected at week 8 to ensure that participants with documented gluten exposure are distributed equally between the blinded and open results arms. Participants in the open results arm will receive instruction in using home test kits for detection of GIPs and supplied with test kits to be used at home during the remainder of the study period. Participants will be given a parking voucher and receive a \$30 ClinCard as a token of appreciation. All participants will also have a diet assessment by a Registered Dietitian either in person or remotely by telephone or video link in conjunction with the week 8 study visit.

During weeks 8 through 30, participants will keep a diary of any suspected gluten exposures. Participants will be contacted by the study co-ordinator at random intervals (approximately every three to four weeks) and instructed to collect their next urine and complete the symptom questionnaire. Participants in the open results arm will also perform home testing and send a photo of the test results to the study co-ordinator to document results and confirm test completion. Used test kits may be disposed in household trash. Participants will also test up to 4 stool samples during this time that will be collected and tested at the discretion of the participant. Participants will report date of use, results,

and reason for use after each home stool test. Participants will return all other study materials and containers at the final study visit.

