#### **(6) Study Timeline (as applicable)**

- Eligibility Screening
  - Participants who are eligible for this study will be identified when they are scheduled for an outpatient clinical appointment for follow-up of celiac disease
  - Potential participants will be contacted and informed of the study. If they express that they may be interested in participating, they will be asked to provide verbal consent to receive sample collection materials and a copy of the consent form.
  - urine sample (from a first morning void if possible) will be collected. Optional stool sample collected.
- Recruitment Visit (week 1) in conjunction with a scheduled outpatient clinic appointment for follow-up of celiac disease
  - written informed consent
  - provide stool and urine samples (may be collected prior to visit)
  - patient/parent self-report questionnaire
  - height and weight
  - blood draw: TTG, DGP, CBC, stored samples for makers of gluten-free diet adherence, celiac disease activity and nutrition.
  - Participant receives a parking voucher
- At home (weeks 1 through 7)
  - collect additional urine samples and complete questionnaire when contacted by study coordinator at random intervals (x2)
  - keep a diary of suspected/probable gluten exposures.
  - collect an additional stool sample during week 8 (to be used at week 8 study visit for randomization)
- Study Visit 2: (week 8)
  - Return samples and questionnaires completed at home when prompted.
  - Bring additional stool sample collected during week 8 (for randomization)
  - Randomization to blinded or open test results.
  - patient/parent self-report questionnaires
  - height and weight
  - Participant receives parking voucher and \$30 ClinCard as a token of appreciation
  - Diet assessment, either in person or remotely by telephone or video link
- At home (weeks 8 through 30)
  - collect additional urine samples and complete questionnaire when contacted by study coordinator at random intervals (x6, approximately every four weeks)
  - keep a diary of suspected/probable gluten exposures
  - Use of stool kits at participants discretion (x0-4)

- Final study visit (week 30)
  - Return samples and questionnaires completed at home.
  - Complete quality of life and symptom questionnaires.
  - Diet assessment, either in person or remotely by telephone or video link.
  - Height and weight

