#### *Secondary outcomes*

Outcomes related to gluten exposure will be considered as continuous variables and also converted to categorical variables. The per individual change in frequency of gluten exposure will be determined by calculating the difference in the proportion of GIP positive urine samples in the pre-randomization (weeks 1, 2, and 4) and post-randomization (weeks 8 through 30) samples. The same visits will be used to calculate the per individual change in mean quantity of gluten exposure pre- and post-randomization. Results will be categorized as decreased, no change or increased frequency/mean concentration of gluten exposure.

Symptom and quality of life scores are also continuous variables and group comparisons will be assessed using a paired t-test. The PedsQL 4.0 Generic Subscales has 23 items across four subscores (physical, emotional, social and school functioning) and scores are scaled to range from 1 to 100. The scale has been validated for children aged 5 to 18 and the minimally clinically important difference (MCID) is 4.4 for child report and 4.5 for parent report. The CDDUX has 12 items and three subscores related to diet, communication and having celiac disease. It is also scaled from 1 to 100 and has been shown to correlate with perceptions of disease severity.

Agreement between results of patient/parent performed qualitative testing and quantitative testing performed by research team will be assessed using McNemer's test (qualitative testing) or intraclass correlation (quantitative testing).

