### **I. Statistical Power and Sample Considerations**

The primary outcome is the difference in rate of gluten detection in the six urine samples provided after randomization (weeks 8 through 30) between the blinded and unblinded groups. A total sample of 102 (n=51 in each group) provides 90% power to detect a difference of 50% gluten detection in the blinded group versus 25% gluten detection in the open results group, given six outcomes per participant with an intraclass correlation of 0.6 and alpha set at 0.05. Given a more conservative intraclass correlation of 0.8, we will still have 82% power to detect the predicted effect size. If participants are more highly adherent, then this sample size should also be sufficient as fewer participants will be required. For example, using the same assumptions for intraclass correlation, with 43 subjects in each group there is 90% power to detect a difference of 40% gluten detection in the blinded versus 25% gluten detection in the open results group (alpha = 0.05).

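### McNemar's test, named for home-versus-laboratory agreement, tests only equal positive rates, and the quantitative intraclass correlation does not fit a yes/no home kit

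*Protocol*

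**What the plan says.** The list of secondary outcomes in section D(4) of the protocol includes "Agreement between results of patient/parent performed qualitative testing and quantitative testing performed by research team". Section H, under secondary outcomes, gives the analysis as McNemar's "test (qualitative testing) or intraclass correlation (quantitative testing").

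Section D(3) says that open-arm families get kits so that they may "receive immediate qualitative (yes/no) feedback regarding the presence of biomarkers of gluten exposure". Section D(5) confines this to one arm: "Participants in the open results arm will also perform home testing and send a photo of the test results".

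No percent agreement, kappa, sensitivity or specificity is named for this outcome anywhere in the protocol. The general part of section H does provide for turning continuous measures into categories, with peptide-negative versus peptide-positive as its example, and for reporting proportions with 95% confidence intervals.

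**The concern.** The outcome is agreement: when a family reads a kit as positive or negative, does the laboratory find the same in that sample? McNemar's test answers a different question, namely whether the two methods have the same overall positive rate. A home test that misses many true positives and raises about as many false alarms would show no difference. A reader could take that as evidence that the kit agrees with the laboratory.

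The second method named needs two readings on a common quantitative scale, and the home kit supplies none.

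At stake is how one secondary result is read. It matters because the home result is the feedback that open-arm families receive during the trial, so its agreement with the laboratory assay bears on how the intervention is understood.

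**Working it through.** The protocol gives no figure for this analysis, so there is nothing to reproduce. The check shows what the named methods return for given data.

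**Inputs from the protocol**
- Section I: "A total sample of 102 (n=51 in each group"), hence 51 children in the open arm.
- Section D(6): post-randomization urine samples are collected "at random intervals (x6, approximately every four weeks").
- Section I: "25% gluten detection in the open results group, given six outcomes per participant", used here only to set the laboratory positive rate.
- Section H: two-sided tests at 5%.

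**Assumptions**
- All six urine samples are tested both ways, giving 51 x 6 = 306 pairs. This is a ceiling. Discretionary stool tests are left out.
- The laboratory result is read as detectable or not detectable: 76 of 306 positive (24.8%).
- All cell counts below are illustrative. None comes from the protocol.

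**Formulas.** Let a = both positive, b = home only, c = laboratory only, d = both negative, n = a + b + c + d.
- McNemar's statistic = (b - c)² / (b + c). The exact p-value is a two-sided binomial test of b against c at one half. Neither a nor d enters.
- Positive percent agreement = a / (a + c). Negative percent agreement = d / (b + d).
- Kappa = (Po - Pe) / (1 - Pe), with Po = (a + d) / n and Pe the agreement expected by chance from the margins.

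**Main example, 46 / 30 / 30 / 200**
- McNemar: (30 - 30)² / 60 = 0, p = 1.0.
- Positive agreement: 46 / 76 = 60.5%. Negative agreement: 200 / 230 = 87.0%.
- Po = 246 / 306 = 0.804. Pe = (76/306)² + (230/306)² = 0.627. Kappa = (0.8039 - 0.6267) / (1 - 0.6267) = 0.47.

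The home test misses four in ten laboratory positives, and McNemar's test shows nothing.

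**Exact balance is not needed.** With 60 discordant pairs, a split of 37 to 23 gives (37 - 23)² / 60 = 196 / 60 = 3.27, below the 5% critical value of 3.84. With 37 false negatives, positive agreement is 39 / 76 = 51.3%. With 23, it is 53 / 76 = 69.7%. McNemar's test is non-significant across that whole range.

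**Other assumed tables of 306 pairs**

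| a / b / c / d | Agreement | Kappa | Exact McNemar p |
|---|---|---|---|
| 19 / 57 / 57 / 173 | 62.7% | 0.00 | 1.0 |
| 0 / 76 / 76 / 154 | 50.3% | -0.33 | 1.0 |
| 76 / 0 / 0 / 230 | 100% | 1.00 | 1.0 |
| 66 / 10 / 0 / 230 | 96.7% | 0.91 | 0.002 |

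Chance-level, worse-than-chance and perfect agreement all give p = 1.0. The p-value does not order these tables by agreement, whereas kappa does.

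**Intraclass correlation.** If the 0/1 home result is set against a simulated log-normal laboratory concentration, with every sample classified correctly by the home test, the absolute-agreement intraclass correlation is 0.51, 0.06 and 0.01 when the laboratory unit is multiplied by 1, 10 and 100. It follows the unit, not the agreement.

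**The case against.** Several points on the other side are fair.

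- **McNemar's test is a standard method for paired yes/no data.** It is, for detecting whether one method is positive more often. Suppose the home test misses 7 laboratory positives and makes no opposite errors. Then the exact p is 2 x 0.5^7 = 0.016, with agreement of 299 / 306 = 97.7% and kappa 0.94. A reader might infer a false alarm against an excellent test. That is not so: 7 / 76 = 9.2% of positives missed, all in one direction, is real under-detection. The test does its own job there, but that job is not measuring agreement.
- **An intraclass correlation can serve for binary data.** A reader might infer that neither named method could ever measure agreement on a yes/no result. That goes too far: on 0/1 scores for the table 66 / 10 / 0 / 230, the intraclass correlation is 0.909 and kappa 0.908. But section H assigns it to quantitative testing, so that use is not what is planned.
- **Part of the remedy is already in the plan.** Section H allows conversion to negative/positive and promises proportions with confidence intervals. This makes the fix easy, but it names no agreement measure and leaves McNemar's test as the stated method.
- **Handling of repeated samples may be in a statistical analysis plan that is not at hand.** This stands. The protocol does not say that pairs will be pooled as independent, so clustering is no separate fault. It belongs in the remedy because a child can supply six pairs, and section I itself assumes a within-child correlation of 0.6 for detection results. The correlation of discordance between the two tests is not given.

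**Conclusion.** The point holds. As written, the analysis would not measure the agreement that the secondary outcome names: McNemar's test compares positive rates only, and the quantitative intraclass correlation has no home reading to work on. In the assumed table, p = 1.0 accompanies positive agreement of 61% and kappa of 0.47. That size rests on illustrative cell counts, full completion of six samples by 51 children and a 25% positive rate. The defect itself does not depend on them.

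The reach is limited. A reader might infer that a study objective is compromised, but the Specific Aims and Hypotheses contain nothing on home-versus-laboratory agreement; it is one item in the secondary outcome list. The primary outcome uses the laboratory assay alone, so neither it nor the sample size is affected. The paired data are collected anyway, so the right measures remain available.

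**What to change.** Replace the sentence in section H with wording to this effect:

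- Classify the laboratory assay as detectable or not detectable, the definition already used for the primary outcome.
- Report positive and negative percent agreement of the home test, with the laboratory as reference, together with kappa.
- Give 95% confidence intervals that allow for several samples per child, for example by a child-level bootstrap or a robust variance.
- Drop the intraclass correlation for quantitative testing.
- Keep McNemar's test only as a supplementary check for directional bias, and say so.

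The cost is a few lines of analysis text, with no new data, visits or participants.

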### **I. Statistical Power and Sample Considerations**

The primary outcome is the difference in rate of gluten detection in the six urine samples provided after randomization (weeks 8 through 30) between the blinded and unblinded groups. A total sample of 102 (n=51 in each group) provides 90% power to detect a difference of 50% gluten detection in the blinded group versus 25% gluten detection in the open results group, given six outcomes per participant with an intraclass correlation of 0.6 and alpha set at 0.05. Given a more conservative intraclass correlation of 0.8, we will still have 82% power to detect the predicted effect size. If participants are more highly adherent, then this sample size should also be sufficient as fewer participants will be required. For example, using the same assumptions for intraclass correlation, with 43 subjects in each group there is 90% power to detect a difference of 40% gluten detection in the blinded versus 25% gluten detection in the open results group (alpha = 0.05).

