Other antibodies have also been described, including G12, which recognizes the principal antigenic sequence in gliadin (PQPQLPYP). The G12 antibody has been used to determine the gluten content of beer as well as to detect gluten in the stool and urine. Initially, a graded gluten challenge protocol was used to determine the relationship between the amount of gluten ingested and the amount of gluten immunogenic peptides (GIPs) detected in fecal extracts using an ELISA technique. Using the G12 monoclonal antibody, GIPs could be detected in stool after ingestion of as little as 50 mg of gluten (equivalent to a penne noodle). This amount is clinically relevant as estimated ingestion of as little as 10-50 mg of gluten per day has been associated with mucosal damage in patients. The time from ingestion to excretion of gluten peptides in stool was observed to be between 2 and 4 days.

In subsequent study of 188 patients with celiac disease on a GFD, 73 positive controls on a gluten-containing diet and 11 negative controls (formula fed infants who had not been exposed to gluten), the sensitivity and specificity of GIP testing in stool were 98.5% and 100%, respectively. Among patients with celiac disease on a gluten-free diet, 30% had detectable levels of GIP in their stool, of whom 70% appeared to be adherent based upon self-report questionnaire and four day food record. It is unknown how these tests perform in a clinical setting.

Further studies have demonstrated that GIPs are also excreted in urine within 24 to 48 hours of ingestion. Similar to studies of stool, the test had excellent sensitivity with detection of ingestion of as little as 25 mg of gluten.

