## **H. Data Analysis Plan**

For all outcomes, descriptive data analysis will be used to assess variables' distributions and to detect outliers and influential observations. We will estimate means (and standard deviations) and medians (and interquartile ranges) of continuous variables, and proportions of categorical variables. In addition, we will examine the data using plots, such as boxplots, histograms and smoothed-scatterplots. When necessary, variables will be transformed to meet assumptions for statistical tests. All statistical tests will be two-sided and will use a Type I error of 5%. For confidence intervals, we will use two-sided 95% coverage probabilities.

As a general approach, all proportions will be reported as mean with the associated 95% confidence interval for the estimate. This will provide more meaningful information about the precision of each estimate as well as the possible clinical significance of any observed differences in the mean value. As such, p values for comparisons of means will not be determined with the implicit assumption that values for which the 95% confidence intervals overlap do not differ significantly. Relationships between continuous measures will be analyzed using Pearson's correlation coefficient. Where appropriate,

continuous measures will also be converted to categorical variables (e.g., serum antibody negative/positive vs. GIP negative/positive).

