#### *Primary outcome*

For the primary outcome, gluten exposure is defined as percentage of samples collected between weeks 8 and 30 with detectable gluten immunogenic peptides using the quantitative assay. Differences in gluten exposure between the blinded and open results groups will be assessed using the chi-squared test.

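### The second power example (43 per group, 40% versus 25%, 90% power) is wrong as printed: the protocol's own method gives about 44%, and the 25% is probably a misprint for 15%

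*Protocol*

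**What the plan says.** Section I of the protocol (Statistical Power and Sample Considerations) sizes the trial on one scenario: "A total sample of 102 (n=51 in each group) provides 90% power to detect a difference of 50% gluten detection in the blinded group". The open-arm rate in that scenario is 25%, each child contributes six urine samples, the ICC is 0.6 and alpha is 0.05. At an ICC of 0.8 the stated power is 82%.

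The section then makes a general claim about lower exposure: "If participants are more highly adherent, then this sample size should also be sufficient as fewer participants will be required". The one example given in support keeps the same ICC assumptions and alpha: "with 43 subjects in each group there is 90% power to detect a difference of 40% gluten detection in the blinded versus 25" per cent in the open results group.

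Section H (Data Analysis Plan) fixes the test. It says "All statistical tests will be two-sided and will use a Type I error of 5" per cent, and for the primary outcome "Differences in gluten exposure between the blinded and open results groups will be assessed using the chi-squared test".

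**The concern.** The two scenarios share the open-arm rate (25%), the number of samples per child, the ICC, alpha and the target power. They differ in the blinded-arm rate, so the difference to be detected falls from 25 points to 15. Yet the required number per group falls from 51 to 43. The binomial variance is only slightly smaller at 40% than at 50% (0.24 against 0.25), which cannot offset a 40% cut in the difference. The example therefore conflicts with the main calculation before any power is computed.

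It matters because this is the protocol's only statement about power when gluten exposure is less common than assumed. A reader who accepts it would regard a true 40% versus 25% contrast as well covered by 102 children.

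**Working it through.** **Inputs, all from Protocol Sections H and I.** Two-sided alpha 0.05 (z = 1.960); chi-squared comparison of two proportions; 1:1 allocation; six urine samples per child; ICC 0.6, or 0.8 in the conservative case.

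**Formulas.** The design effect is 1 + 5 × ICC, which is 4 at ICC 0.6 and 5 at ICC 0.8. The effective number of samples per group is m = 6n / (1 + 5 × ICC). With d = p1 − p2 and p̄ the mean of the two rates:

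power = Φ{ [d√m − 1.960 √(2p̄(1 − p̄))] / √(p1(1 − p1) + p2(1 − p2)) }

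**Step 1: reproduce the main scenario (50% versus 25%, n = 51).**
- ICC 0.6: m = 306/4 = 76.5. Power = Φ[(0.25 × 8.746 − 1.960 × 0.6847)/0.6614] = Φ(1.277) = 89.9%. Stated: 90%.
- ICC 0.8: m = 306/5 = 61.2. Power = Φ[(0.25 × 7.823 − 1.342)/0.6614] = Φ(0.928) = 82.3%. Stated: 82%.

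Both figures match, so this is in effect the protocol's own method.

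**Step 2: apply it to the second example as printed (40% versus 25%, n = 43).**
- ICC 0.6: m = 258/4 = 64.5. Power = Φ[(0.15 × 8.031 − 1.960 × 0.6624)/0.6538] = Φ(−0.143) = 44.3%.
- ICC 0.8: m = 258/5 = 51.6. Power = 36.8%.
- With the planned 51 per group: 50.8% and 42.4%.
- Samples needed for 90% power: m = [(1.2982 + 1.2816 × 0.6538)/0.15]² = 202.8. At ICC 0.6, n = 202.8 × 4/6 = 135.2, so 136 per group. At ICC 0.8, n = 202.8 × 5/6 = 169.01, so 170 per group.

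**Step 3: see whether another convention rescues 90%.** For n = 43 and ICC 0.6, unpooled variance gives 45.3%, continuity correction 36.9%, arcsine 44.8%, log-odds 43.9%, and a one-sided test 57.0%. A beta-binomial simulation (20,000 runs, t-test on per-child proportions) gives 44.3%. With the two-sided test, an ICC of 0.1 still gives only 84.7%. Power passes 90% only when samples are close to independent (95.5% at ICC 0), which contradicts the stated ICC.

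**Step 4: find the rates that 43 fits.** With 40% in the blinded arm, n = 43 and ICC 0.6, 90% power is reached when the open-arm rate is 14.9%. Taking 40% versus 15%:

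| Per group | ICC 0.6 | ICC 0.8 |
|---|---|---|
| 43 | 89.8% | 82.1% |
| 51 | 94.1% | 88.2% |

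The required m is [(1.2377 + 1.2816 × 0.6062)/0.25]² = 64.9, so n = 64.9 × 4/6 = 43.3. The same step for 50% versus 25% gives m = 76.7 and n = 51.1. Both printed group sizes are therefore these values rounded to the nearest integer.

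**The case against.** The strongest reply is that this is a one-number slip in a secondary illustration. At 40% versus 15% the example gives the same pair of powers as the main scenario and keeps the same 25-point difference. On that reading it is correct, and it is true that fewer children are needed. The trial's size rests on 50% versus 25%, which reproduces at both ICCs; the example sets neither enrolment, endpoint nor analysis. Most of this stands, and it limits the seriousness of the point. It does not remove it: the misprint is inferred from the arithmetic, and the printed power is wrong whatever the cause.

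Three stronger readings are tempting but unsupported.

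- **That the trial is undersized.** The main calculation is sound on its own assumptions, so the documents do not show this.
- **That the sufficiency sentence is false in any case, because halving the rate needs more children as the control rate falls.** With 51 per group and ICC 0.6, power is 78% for 40% to 20%, 60% for 30% to 15% and 41% for 20% to 10%. Those figures are correct, but the protocol specifies absolute rates and never says that the relative effect is constant.
- **That the trial should expect about 30% in the blinded arm.** Section C does report that "Among patients with celiac disease on a gluten-free diet, 30% had detectable levels of GIP in their stool", but that is stool from another cohort, with excretion at 2 to 4 days. The powered outcome is urine, with excretion within 24 to 48 hours. The figure shows that rates below 50% are worth considering; it does not estimate the urine rate here.

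**Conclusion.** The point holds, narrowly. The stated 90% power for 43 per group at 40% versus 25% is wrong. Under the protocol's ICCs it is 44% (ICC 0.6) or 37% (ICC 0.8), and no standard variant at ICC 0.6 exceeds 57%. For the rates as printed, 102 children give about 51% or 42% power, so the example does not support the claim that the sample also suffices.

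The likely explanation is that the open-arm rate should read 15%; only the sponsor can confirm this. If so, the sufficiency claim is true when the absolute difference stays at 25 points, and unsupported beyond that. These results assume six samples from every child, equal groups and a common ICC, as Section I does. This is an error to correct in the text, not a defect in the main sample size.

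**What to change.** The sponsor should check the original calculation and confirm the intended open-arm rate in the second example of Section I.

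- **If 15% was meant:** replace 25% with 15%, and limit the preceding sentence to the case where the absolute difference stays at 25 points. The protocol could add that 51 per group then give 94% power at ICC 0.6 and 88% at ICC 0.8.
- **If 25% was meant:** restate the power at ICC 0.6 as 44% with 43 per group, or 51% with 51 per group, and delete the sentence claiming that the sample would also suffice.

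A short table of power at 51 per group under a constant relative effect would help readers, but it is optional.

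The cost is a wording change. The total of 102 and its justification at 50% versus 25% stay as they are. The only downside is a narrower or less favourable statement of robustness.
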